4.6 Duration of Study

Several CT volumetric studies will be performed for each enrolled subject: one before the radiotherapy course for patient treatment planning purposes (as part of the standard of care), one during the radiotherapy treatment course (between fraction 10 and 20 for 3DCT, IMRT or VMAT patients and after fraction 3 for SBRT patients), and one at follow up visit or at least 6 weeks post-radiotherapy treatment(whichever comes first). The acquisition of these imaging data will require approximately 15 additional minutes of the patient time at those visits.

5.0 DOSE MODIFICATIONS

There will be no immediate benefit to the patients from the performed research, since their course of treatment will not be affected by the proposed prospective data collection. However, an exception might occur if during the CT scans throughout the course of treatment a large tumor response (e.g. tumor regression) or normal tissue changes are discovered. Such a finding may prompt a radiotherapy treatment plan adaptation, which will be left at the discretion of the attending physician.

6.0 DATA ANALYSES PLAN

This clinical imaging study will form a database for future research and development of 3D and 4D treatment planning approaches for different anatomical sites treated with radiotherapy. Statistical analyses will be used to assess the differences among standard of care, realized through DVHs, and our newly proposed mass-based optimizations and DMH evaluations. Those statistical analyses are powered to detect clinically significant differences in dosimetry and estimated clinical outcome endpoints between various proposed simulated treatment techniques. Significant changes include:

- Dosimetric: a dose variation between the different treatment planning approaches for normal tissue structures of more than 7%.
- Estimated clinical outcome: a $\geq 5\%$ variation of normal tissue toxicity using the generalized equivalent uniform dose (gEUD) metric and isoeffect parameters and analyses tools developed by the NCI funded R01 CA163370 research grant.

We will start with the null hypothesis that no difference between the treatment planning approaches is observed for the dosimetric and the estimated clinical outcome endpoints. Since patients are treated according to the standard of care and only their imaging information is used to estimate the potential outcome benefit of the new planning approaches, each patient serves as a control for themselves. Results will therefore be paired. The differences between the standard of care inverse optimization

and the proposed mass-based schemes for tumors will be tested using one-tailed paired *t*-tests, against a hypothesis that $\pm 3\%$ radiation dose differences in the tumors will not have an observable clinical significance. The differences between the optimization results on the remaining parameters for all healthy anatomical structures (within the radiation field) will be tested using standard two-tailed *t*-tests with the null hypothesis set to 0%. We anticipate an enrollment period of five years.

7.0 DATA AND SAFETY MONITORING PLAN

This study is a non-therapeutic study. As described in section 8.4 below the risks to the patients are very minimal, given that all of the enrolled individuals will receive radiation therapy as a standard of cancer care. No adverse events are expected within the scope of our work. Therefore, the data safety monitoring for this study would be performed by the PI and the co-investigators. The research team bears responsibility for suspending or terminating this study.

8.0 HUMAN SUBJECTS INSTRUCTIONS

8.1 SUBJECT POPULATION

Data would be utilized from all Department of Radiation Oncology at UM patients >18 year old with histologically proven head-and-neck, lung, and prostate cancers who will be treated with 3DCT, IMRT, VMAT, and SRT.

8.2 RESEARCH MATERIAL

Along with the CT imaging studies and the physical description of the radiotherapy, the following data will be collected as well from each subject:

MRI studies (if any)	Toxicities
PET-CT studies (if any)	Prior Surgery
Age	Tumor location
Performance status	Diagnostic CT/MRI/PET report
Histology	Tumor volume
Disease stage	Medication
Patient weight	Critical structures

All of the data recorded will be entered into a database maintained by the principal investigator. Majority of that data for each patient is part of either our “record and verify” system or UChart. This data includes patient age, performance, histology, disease stage, patient weight, prior surgery, diagnostic report, medication. It will be

transcribed either by the PI or the study staff. For toxicity we will use CTCAE 4.0 grading system (cf. Appendix II). Tumor volume and location as well as volumes and locations for all adjacent healthy anatomical structures within the radiation field would be determined from the radiotherapy treatment plans used for patient therapy.

8.3 RECRUITMENT PLAN

All eligible patients will be informed of the opportunity to participate in this study by the attending radiation oncologist. Eligibility will be determined by a completion of an eligibility checklist. Specific details of the study, including a copy of the informed consent will be provided to all potential subjects. Informed consent can be obtained by the attending radiation oncologist, principal investigator, or study coordinator at initial consult or at any time prior to radiation therapy planning. The patient will have the opportunity to have any questions answered by any of the co-investigators or study staff involved. Subjects must document their consent to participate by signing a written informed consent form that includes HIPAA authorization and has been approved by the University of Miami IRB.

8.4 POTENTIAL RISKS

The CT imaging studies proposed in this study do not subject patients to any therapeutic intervention beyond what is prescribed as part of their routine clinical care. A synopsis of radiation doses from the proposed imaging studies to be delivered to each subject enrolled in this protocol is presented in Table 1. The data outlines the CT imaging dose from a single CT scan. This data is for a 4D CT scan. 4D CT scans deliver more radiation than much more commonly used 3D CT scans. Therefore, the presented dose estimates are effectively for upper dose limits. 4D CT scanning is relevant only for lungs patients. For head-and-neck and prostate patients standard 3D CT protocols will be used. As mentioned above, the 3D CT scans result in somewhat lower radiation doses than those outlined in Table 1.

Table 2 presents the data for cone beam CT (CBCT) and on-board imagers (OBI), used on daily basis for patient positioning and pre-treatment localization. The cumulative doses in the table are calculated for a standard 35 session course of treatment, aiming to deliver radiation dose between 6600 cGy and 7000 cGy (depending on the fractional dose) to the tumor(s). In those 35 treatments there will be 7 CBCTs (once per week), while the remaining 28 treatments will utilize OBI for patient positioning. If a patient undergoes a SRT treatment, then all 3 to 5 fractions (which comprise this treatment) will require the use of CBCT.

The risk to the participants in our prospective CT data collection is very minimal. The therapeutic doses delivered to cancer patients are of the order of 200 cGy in each daily fraction. It is evident from Table 1 that imaging dose of ~4 cGy, delivered through a 4D CT scan, is ~ 2% of that daily dose. Notably, 2% daily variation in the radiation output is within the operational specifications of modern linear accelerators. In other words the added imaging dose per one CT scan will be no larger than the stochastic variation of the daily machine output. Furthermore, Table 2 demonstrates that the dose resulting from 7 CBCT and 28 OBI applications, used as standard of care for accurate patient daily localization, is equivalent to four 4D CT studies, i.e. one more study than the proposed number in this protocol (we will subject patients to one CT which is standard of care and two more for research purposes).

In summary, the addition of three 3D or 4D CT scans in our prospective data collection will have a negligible dosimetric effect on the patients, given that it is only 6% of a single fractional (daily) dose, or less than 0.2% of the total prescription dose over the course of treatment comprised by 35 fractions.

Table 1: Radiation Doses from CT Imaging

Scanning protocol	Depth of measurement [cm] (corresponding anatomical structure)	Dose [cGy]
4D	1 (chest wall)	3.5
4D	8 (heart)	2.2
4D	12 (lung)	1.7
3D large chest	1 (chest wall)	3.0

Table 2: Radiation Doses from CBCT and OBI Imaging

Type of imaging	# of imaging sessions	Estimated dose per session	Estimated total dose
CBCT	7	0.61 cGy (x2)	8.54 cGy
CBCT (SBRT)	5	0.61 cGy (x2)	3.05 cGy
OBI	28	0.08 cGy (x4)	8.96 cGy

8.5 SAFEGUARDS IF ANY PARTICIPANTS WILL BE VULNERABLE

Data will be anonymized.

8.6 PRIVACY

Once the patient name and medical record number is removed from the data, there is nothing in that data which could be used to identify patients.

8.7 RISK/BENEFIT

As discussed above, the risk of participating in this study is negligible, except for the inconvenience of spending extra time for additional CT imaging. This study is part of an effort to develop and investigate new methods for inverse radiotherapy plan optimization, which will significantly improve treatment plan quality and therefore reduce volumes and doses to normal tissue to be irradiated. Our studies will benefit future patients receiving radiation therapy for cancer treatment, but the patients enrolled in this study however will not directly benefit from the newly developed approaches. This is not a therapy study. Attending radiation oncologists may use this imaging data to improve the participating subject's therapy, provided that all applicable FDA and IRB guidelines are followed.

9.0 CRITERIA FOR DISCONTINUATION

- Attending physician finds it necessary for patient's health or safety.
- Patient decides to withdraw from the study.
- The sponsor discontinues the study.
- Administrative reasons require patient withdrawal.

Although collecting new information about the subject will be stopped, the study team may still use the information they have already collected to evaluate the study results.

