2.0 STUDY OBJECTIVES

2.1 Primary objectives

- To study and evaluate whether DMHs are better suited for predicting radiotherapy response and/or complication (toxicity) than standard of care realized through DVHs.
- To investigate the time-trending changes between patient anatomy and DMH inverse radiotherapy optimization.

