3.3.2 Withdrawal Guidelines

Patients can withdraw at any time if they decide to do so. If, for any reason, the attending radiation oncologist decides that patient participation in the study is not in their best interest the subject will be withdrawn from the study. Furthermore, if the PI decides to discontinue the study, subjects' participation will end. Patients who are enrolled on study but not treated will be excluded from all analyses.

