10.0 DATA REPORTING

Data will be submitted according to the protocol requirements for ALL patients registered. Patients for whom documentation is inadequate to determine eligibility will generally be deemed ineligible. A computer based solution will be implemented to maintain a complete record of subject and study information and all processing. Additional files will be used to maintain a record of all subjects grouped within a single project. For the purposes of evaluating the mass-based effects on treatment planning and treatment plan assessment, we will add the following items in the data-management system: (1) Images with outlined treatment volumes for targets and critical structures; (2) Images with outlined for targets and critical structures before, during, and after radiotherapy; (3) TCP, NTCP calculations, dose-volume histograms, dose-mass histograms, gEUDs, and mgEUDs; (4) isdose volumes and isdose masses; (5) Physician reports from follow-up exams.

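### Any discontinuation, including one by the physician for health or safety, ends all new data collection, so later toxicity, a primary-objective outcome, goes unrecorded and the loss may be selective

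*Combined protocol and SAP*

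**What the plan says.** Section 9.0 gives four reasons for discontinuation: "Attending physician finds it necessary for patient's health or safety"; "Patient decides to withdraw from the study"; "The sponsor discontinues the study"; and "Administrative reasons require patient withdrawal". One sentence then covers all of them, with no exception by reason: "Although collecting new information about the subject will be stopped, the study team may still use the information they have already collected".

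Section 3.3.2 points the same way. If the attending radiation oncologist "decides that patient participation in the study is not in their best interest the subject will be withdrawn from the study". Neither section provides for a patient who is off the research scans but still followed, and no other section does.

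The first primary objective (section 2.1) is to evaluate whether "DMHs are better suited for predicting radiotherapy response and/or complication (toxicity) than standard of care realized through DVHs". Section 8.2 lists toxicities among the data collected from each subject, graded by CTCAE 4.0. Section 10.0 puts physicians' follow-up reports in the study's data system. Section 4.2 describes the study as non-therapeutic, with treatment by standard of care.

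**The concern.** What the study adds to a patient's care is the extra CT imaging. Ending that imaging is a natural consequence of discontinuation. Ending the collection of outcomes is a separate step that the imaging does not require, yet the plan joins the two.

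Timing makes this matter. The on-treatment scan falls between fractions 10 and 20, or after fraction 3 for SBRT (section 4.6), so a patient who leaves around then may not yet have shown the toxicity of interest. The dose data already collected stay usable while the later outcome is missing. If the physician's reason for ending participation is the patient's condition, the missing outcomes may differ from the observed ones. The toxicity data behind the first primary objective are at stake.

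**Working it through.** **No figure to reproduce.** The documents state no discontinuation rate, sample size or dropout allowance, so what follows is an illustration.

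**Inputs.**
- p = 30%, symptomatic radiation-induced lung injury (section 1.2.1). It applies to lung only; head-and-neck and prostate are not covered.
- d = share of patients discontinued: 5%, 10%, 20% (assumed).
- RR = risk of toxicity in discontinued relative to retained patients: 1 to 2.5 (assumed).
- All toxicity in discontinued patients is taken to arise after discontinuation. Events graded earlier are kept, so for given d and RR the share lost is an upper limit.

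**Formulas.** The overall rate is p = (1 − d) × r + d × RR × r, where r is the rate in retained patients. Hence
- complete-case rate r = p / (1 − d + d × RR)
- share of events lost = d × RR / (1 − d + d × RR)

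**At RR = 2.**
- d = 5%: r = 0.30 / 1.05 = 28.6%; lost = 0.10 / 1.05 = 9.5%
- d = 10%: r = 0.30 / 1.10 = 27.3%; lost = 0.20 / 1.10 = 18.2%
- d = 20%: r = 0.30 / 1.20 = 25.0%; lost = 0.40 / 1.20 = 33.3%

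**Range over RR** (complete-case rate; share of events lost):

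| RR | d = 5% | d = 10% | d = 20% |
|---|---|---|---|
| 1 | 30.0%; 5.0% | 30.0%; 10.0% | 30.0%; 20.0% |
| 1.5 | 29.3%; 7.3% | 28.6%; 14.3% | 27.3%; 27.3% |
| 2 | 28.6%; 9.5% | 27.3%; 18.2% | 25.0%; 33.3% |
| 2.5 | 27.9%; 11.6% | 26.1%; 21.7% | 23.1%; 38.5% |

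At RR = 1 events are lost but the rate is not biased.

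**Effect on the DMH-versus-DVH comparison.** The objective compares two predictors in the same patients, so a biased rate need not bias the comparison. AUC depends on how each predictor is distributed among patients with and without toxicity. Loss that depends on toxicity alone leaves both distributions unchanged.

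A simulation of 1,000,000 patients shows this. All its settings are assumed: a standard normal underlying dose; DMH and DVH equal to that dose plus noise of SD 0.5 and 0.9; logistic toxicity with intercept −1.0 and slope 0.9, giving a rate of 29.7%.
- No loss: AUC difference, DMH minus DVH, 0.699 − 0.665 = 0.034.
- Loss of 30% of patients with toxicity and 5% of the others: difference still 0.034.
- Loss of 50% of patients with both toxicity and underlying dose above 0.5 SD, and 5% of the others: 0.641 − 0.616 = 0.025.

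The comparison is distorted in the last case, where loss depends on toxicity and dose together.

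**The case against.** Several stronger conclusions are tempting, and the documents do not carry them.

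- A reader might infer that toxicity is lost selectively in the sickest patients. Only one of the four reasons is health-related by its wording, patient withdrawal may or may not be, and no distribution of reasons is given. Selective loss is possible but not established.
- A reader might infer that a patient spared a research CT is thereby withdrawn. Nothing says so. Section 3.3.2 turns on a judgement about participation as a whole, which adds about 15 minutes at the scan visits (section 4.6). Section 4.3 also lets a clinically ordered CT replace a research one.
- Section 10.0 might be read as contradicting section 9.0: "Data will be submitted according to the protocol requirements for ALL patients registered". The requirement is qualified by what the protocol requires, and section 9.0 is part of the protocol, so the two can be read together.
- Loss of safety oversight does not follow. Section 7.0 expects no adverse events within the scope of the study, and a discontinued patient has no further study exposure.
- Nor can one assume that discontinued patients would be counted as free of toxicity. No section says so, and section 6.0 sets out no analysis of observed toxicity.

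Two further objections stand as limits. That toxicity could be read from routine records is an inference: section 8.2 says most data come from existing clinical systems, but toxicity is not among the items it names there. And the paired tests in section 6.0 use dose and estimated outcome (gEUD), not observed toxicity, so this rule does not remove observed outcomes from them.

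What remains is the rule itself. It covers every reason, and nothing elsewhere softens it.

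**Conclusion.** The point holds as a gap in outcome collection that is cheap to close. As written, toxicity that arises after any discontinuation is not recorded, although it belongs to the first primary objective. The loss may be selective. It would bias the toxicity rate if discontinued patients are at higher risk than retained ones, and the DMH-versus-DVH comparison if loss depends on both toxicity and dose.

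The size is unknown because no discontinuation rate is given. In the lung illustration at a risk ratio of 2, the complete-case rate falls by 1.4 to 5.0 percentage points from 30% as discontinuation goes from 5% to 20%. That rests on assumed values of d and RR and on toxicity arising after discontinuation.

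**What to change.** In sections 9.0 and 3.3.2, separate stopping research CTs from stopping data collection.

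- When an individual patient is discontinued by the physician or for administrative reasons, stop only the research CTs. Keep abstracting toxicity, response and follow-up reports from the routine record through the follow-up used for other patients, as consent and HIPAA authorization allow. State that period, because the calendars in Appendix I have no toxicity row.
- Stop new collection when the patient withdraws that permission or the whole study is ended.
- Record the reason and date of each discontinuation, so that the pattern of loss can be examined.

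The cost is protocol and consent wording and a little more chart abstraction. No visits or scans are added.

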10.0 DATA REPORTING

Data will be submitted according to the protocol requirements for ALL patients registered. Patients for whom documentation is inadequate to determine eligibility will generally be deemed ineligible. A computer based solution will be implemented to maintain a complete record of subject and study information and all processing. Additional files will be used to maintain a record of all subjects grouped within a single project. For the purposes of evaluating the mass-based effects on treatment planning and treatment plan assessment, we will add the following items in the data-management system: (1) Images with outlined treatment volumes for targets and critical structures; (2) Images with outlined for targets and critical structures before, during, and after radiotherapy; (3) TCP, NTCP calculations, dose-volume histograms, dose-mass histograms, gEUDs, and mgEUDs; (4) isdose volumes and isdose masses; (5) Physician reports from follow-up exams.

11.0 INVESTIGATOR'S RESPONSIBILITIES

11.1 Investigator Responsibility/Performance

The investigator will ensure that this study is conducted in accordance with all regulations governing the protection of human subjects.

The investigator will ensure that all work and services described in, or associated with, this protocol will be conducted in accordance with the investigational plan, applicable regulations, and the highest standards of medical and clinical research practice.

11.2 Confidentiality

To safeguard confidentiality, imaging data for patient enrollees will be transferred to a computer workstation which is password-protected and kept in a locked room,

accessible only to institutional personnel. Image data sets will be de-identified by a coding system that assures (a) subsequent image displays contain no patient identifiers and (b) file names are free of patient identifiers. Patient-specific images and other data will be coded using three digit incrementing ID numbers (001, 002, etc.) assigned in order of accrual to the study. The master list documenting association between actual patient name and ID number will be accessible only to the PI. All data will be stored in secure locations on the University of Miami network (i.e., inside the University of Miami firewall).

11.3 Informed Consent and Permission to Use Protected Health Information

It is the responsibility of the investigator(s) to obtain written informed consent from each subject participating in this study after adequate explanation, in lay language, of the methods, objectives, anticipated benefits, and potential hazards of the study. The investigator(s) must also explain that the subject is completely free to refuse to enter the study or to discontinue participation at any time (for any reason). Prior to study enrollment, each subject will sign an IRB approved informed consent form and receive a copy of it (and information leaflet, if appropriate). For subjects not qualified or able to give legal consent, consent must be obtained from a parent, legal guardian, or custodian.

The investigator or designee **must** explain to the subject before enrollment into the study that for evaluation of study results, the subject's protected health information obtained during the study may be shared with the study sponsor, regulatory agencies, and the IRB. It is the investigator's (or designee's) responsibility to obtain permission to use protected health information per HIPAA from each subject, or if appropriate, the subjects' parent or legal guardian.

11.4 Source Documentation and Investigator Files

The investigator must maintain adequate and accurate records to fully document the conduct of the study and to ensure that study data can be subsequently verified.

